### **Serious Adverse Event (SAE)**

SAEs are determined by the flag on the Adverse Events eCRF page.

### **Treatment-Related Adverse Event**

Treatment-emergent adverse event is defined as treatment-related, if investigator considered it as having a reasonable possibility to be related to study treatment, which is reflected in the eCRF with a corresponding flag.

### **Adverse Event leading to dose adjustment**

Adverse event is defined as leading to dose adjustment if at least one of the following actions was taken with the study treatment due to AE:

- dose increased
- dose reduced
- drug interrupted
- drug withdrawn

### **Adverse Event leading to pausing in uptitration**

Adverse event leading to pausing in uptitration are determined by the flag on the Adverse Events eCRF page.

### **Columbia-Suicide Severity Rating Scale (C-SSRS)**

The Columbia-Suicide Severity Rating Scale (C-SSRS) is a questionnaire that prospectively assesses Suicidal Ideation and Suicidal Behavior based on following categories:

#### **Suicidal Ideation**

- Cat. 1 - Wish to be dead
- Cat. 2 - Non-specific active suicidal thoughts
- Cat. 3 - Active suicidal ideation with any methods (not plan) without intent or act
- Cat. 4 - Active suicidal ideation with some intent to act, without specific plan
- Cat. 5 - Active suicidal ideation with specific plan and intent

#### **Suicidal behavior**

- Cat. 6 - Actual attempt (non-fatal)
- Cat. 7 - Interrupted attempt
- Cat. 8 – Aborted or self-interrupted attempt
- Cat. 9 - Preparatory acts or behavior
- Cat. 10 - Suicide

The C-SSRS is administered at each visit, including unscheduled visits. Two versions depending on the type of visits will be used in this study: Screening and Since Last Visit. Please refer to [C-SSRS scoring](#) for scoring details.

#### **Duration of exposure to Test-IMP**

For all calculations of exposure, dose date refers to receiving dose > 0.

The duration of exposure to test-IMP is computed as

$$\text{min (last IMP syringe dose date + 27, EoS date)} - \text{first IMP syringe dose date} + 1.$$

#### **Duration of exposure to control-IMP (tapering off phase included)**

For all calculations of exposure, dose date refers to receiving dose > 0.

The duration of exposure to control-IMP is computed as

$$\text{last IMP tablet dose date} - \text{first IMP tablet dose date} + 1.$$

#### **Duration of exposure to control-IMP out of tapering off phase**

For all calculations of exposure, dose date refers to receiving dose > 0.

The duration of exposure to topiramate out of tapering off phase is computed as

$$\text{last IMP tablet dose date out of tapering off phase} - \text{first IMP tablet dose date} + 1$$

### **Subject Incidence**

The subject incidence for a given event in a given period is defined as the number of subjects with at least one reported occurrence of the event divided by the number of subjects who entered that period. For subjects with multiple occurrences of the same event, the event will only be counted once per subject.

## **2.2 Analysis sets**

**The Randomized Set (RS)** will consist of all participants who received a randomization number, regardless of receiving study medication.

**The Full analysis set (FAS)** will consist of all participants who received at least one dose of active study medication. In FAS, subjects will be analyzed according to randomized treatment, regardless of the actual treatment received.

**The Safety analysis set (SAF)** will consist of all randomized subjects who received at least one dose of active study medication and will be analyzed based on actual treatment received.

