8.5 Adjudication Committee

Not required.

9 Data analysis

The first analysis will be conducted on all patient data when the double-blind treatment epoch of the trial ends. The data will be analyzed by Novartis and/or by the designated CRO.

Analysis sets

The Randomized Analysis Set (RAS) will consist of all participants who received a randomization number, regardless of receiving study medication.

The Full analysis set (FAS) will consist of all participants who received at least one dose of double-blind study medication. In FAS, subjects will be analyzed according to randomized treatment, regardless of the actual treatment received.

The Safety analysis set (SAF) will consist of all randomized subjects who received at least one dose of investigational product and will be analyzed based on actual treatment received.

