9.3 Analysis of the primary variable(s)

9.3.1 Variable(s)

The analysis of the primary variable will be based on the following estimand:

- Population – Safety Analysis Set (SAF)
- Variable of Interest: The primary endpoint is the rate of patients discontinuing the allocated study treatment due to an adverse event (AE) during the double-blind treatment epoch.
- Intervention effect – effect between erenumab versus topiramate during double-blind treatment regardless of adherence to randomized treatment.
- Summary measure – odds ratio

9.3.2 Statistical model, hypothesis, and method of analysis.

The null hypothesis to be rejected is that the odds of AE-related treatment discontinuations are equal in both treatment groups. The corresponding alternative hypothesis is that the odds are not equal under erenumab compared to topiramate.

Let p_j denote the proportion of AE-related treatment discontinuations for treatment group j , $j=0, 1$, where

- 0 corresponds to erenumab
- 1 corresponds to topiramate

The following hypotheses will be tested:

$H_0: (p_1 / (1 - p_1)) / (p_0 / (1 - p_0)) = 1$ versus $H_A: (p_1 / (1 - p_1)) / (p_0 / (1 - p_0)) \neq 1$ In other words:

H_0 : The odds ratio of AE-related treatment discontinuations for erenumab vs topiramate is equal to 1, meaning no difference on AE-related treatment discontinuations between the two treatments. H_A : The odds ratio of AE-related treatment discontinuations for erenumab vs topiramate is different from 1.

The primary analysis will be performed comparing treatments with respect to the primary efficacy variable in a logistic regression model with the factors treatment and stratification factor (migraine days during the baseline epoch). The odds ratio and its 95% confidence interval

(CI) and p-value will be given. The null hypothesis of equal odds will be rejected if the 2-sided p-value from the logistic regression model for the factor “treatment” is <0.05 ; however, superiority of erenumab will be claimed only if the direction is correct, i.e. if the odds of response are lower under erenumab compared to topiramate.

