### 2.5.1 Primary endpoint

The primary endpoint of the study is discontinuation of treatment due to AE during the double-blind epoch of the study.

Analysis on primary endpoint should be done based on Full Analysis Set (FAS).

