### **2.6.1 Secondary endpoint**

The secondary endpoint is an achievement of at least 50% reduction from baseline in MMD over the last 3 months (month 4, 5, and 6) of the double-blind epoch.

The secondary analysis will contrast erenumab versus topiramate in the FAS.

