## **2.8 Safety analyses**

Safety analyses will be based on safety data set (SAF).

All safety analyses will be performed for the Double-Blind Treatment Epoch and Follow-up Epoch separately and in descriptive manner.

Missing data will not be imputed for safety endpoints.

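### Protocol 9.3.1 puts the primary test on an as-treated set and SAP 2.5.1 on an as-randomised one; SAP 2.2 also words entry to both sets differently from the protocol

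*SAP*

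**What the plan says.** **Primary set.** The estimand in Protocol 9.3.1 gives the population as "Safety Analysis Set (SAF"), which Protocol section 9 (Analysis sets) groups by the treatment actually received. The same estimand describes the effect as "during double-blind treatment regardless of adherence to randomized treatment" and defines the variable as stopping the treatment the patient was allocated. SAP 2.5.1 says: "Analysis on primary endpoint should be done based on Full Analysis Set (FAS"). Both documents group the FAS as randomised.

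**Entry rule.** In Protocol section 9 the FAS "will consist of all participants who received at least one dose of double-blind study medication", and the SAF is "all randomized subjects who received at least one dose of investigational product". In SAP 2.2 the FAS "will consist of all participants who received at least one dose of active study medication", and the SAF carries the same active-medication condition.

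**Other uses of the sets.** For the secondary endpoint both documents name the FAS; SAP 2.6.1 says "The secondary analysis will contrast erenumab versus topiramate in the FAS". For other safety data, SAP 2.8 says "Safety analyses will be based on safety data set (SAF").

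**The concern.** The primary endpoint is stopping treatment because of an adverse event, and superiority is claimed from one logistic regression at two-sided 5%. If the protocol groups by treatment received and the SAP by randomisation, two analysts following the two documents could report different odds ratios and p-values. The set and the grouping should be fixed in advance.

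The entry rule matters because the trial is double-dummy: each arm has one active and one placebo component. Under Protocol 5.5.4 staff give the injection from Day 1 and the patient takes the tablets at home; Protocol 5.1.1 puts the first week's tablet in the evening. The active component is therefore the supervised one in the erenumab arm and the unsupervised one in the topiramate arm. A rule that counts only active doses would make exclusion after randomisation depend on the arm. The FAS is the SAP's denominator for both the primary and the secondary analysis.

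**Working it through.** **1. Primary set: members and grouping.** SAP 2.2 gives FAS and SAF the same dosing condition, so within the SAP they hold the same patients. They differ only in where they place a patient whose actual treatment was not the randomised one. The protocol's estimand wording (allocated treatment, irrespective of adherence) fits the as-randomised set better than the as-treated set it names.

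**2. Entry rule: who is kept.**

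| Patient's dosing | Any double-blind dose counts | Only an active dose counts |
|---|---|---|
| Erenumab arm, injection, no tablet | kept | kept |
| Topiramate arm, injection (placebo), no tablet | kept | dropped |
| Erenumab arm, tablet (placebo), no injection | kept | dropped |
| Topiramate arm, tablet, no injection | kept | kept |

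The third row is less likely than the second, because staff inject on Day 1. Exclusion is thus unequal between arms, not confined to one.

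The protocol's SAF term is a third wording. Protocol 5.1.1 lists active and placebo components together as investigational products, so a placebo-only patient would be kept. Protocol 5.5.4 uses the term for the injection. The protocol does not settle it.

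**3. What *active* means in the SAP.** Under First IMP Dose Date (SAP 2.1.1.1), the first sentence ties the date to verum, which supports non-placebo. The second sentence speaks of double-blind IMP, which contradicts it. The SAP is also loose elsewhere: one exposure definition speaks of topiramate for tablets that SAP 2.4.1 summarises as topiramate or placebo.

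**4. Size.** The visible text gives no event rates, so all rates here are assumptions. Inputs: n = 375 per arm (SAP 1.1), unadjusted, events *a* of *n1* on erenumab and *b* of *n0* on topiramate.

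OR = [a/(n1−a)] / [b/(n0−b)]; SE = √[1/a + 1/(n1−a) + 1/b + 1/(n0−b)]; p = 2{1 − Φ(|ln OR|/SE)}.

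*Assumed 5% v 10%* (a = 18.75, b = 37.5):

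| Case | OR | p |
|---|---|---|
| Base: (18.75/356.25)/(37.5/337.5) | 0.474 | 0.011 |
| One topiramate event regrouped to erenumab | 0.513 | 0.021 |
| One topiramate non-event regrouped | 0.471 | 0.010 |
| One erenumab event regrouped to topiramate | 0.437 | 0.005 |
| One erenumab non-event regrouped | 0.476 | 0.011 |
| One topiramate event dropped | 0.487 | 0.014 |
| One topiramate non-event dropped | 0.472 | 0.010 |
| One erenumab event dropped | 0.448 | 0.007 |
| One erenumab non-event dropped | 0.475 | 0.011 |

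At 350 per arm (700 in total, Protocol summary) the base p is 0.014; dropping one topiramate event gives OR 0.488, p 0.018.

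*Assumed 10% v 15%* (a = 37.5, b = 56.25):

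| Case | OR | p |
|---|---|---|
| Base: (37.5/337.5)/(56.25/318.75) | 0.630 | 0.040 |
| One topiramate event regrouped: (38.5/337.5)/(55.25/318.75) | 0.658 | 0.062 |
| One topiramate event dropped: (37.5/337.5)/(55.25/318.75) | 0.641 | 0.049 |
| Two topiramate events dropped: (37.5/337.5)/(54.25/318.75) | 0.653 | 0.060 |

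With whole counts, 38 v 56 events, the base is OR 0.642, p 0.048. Dropping one topiramate event gives p 0.059, and dropping two gives p 0.072.

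*Secondary endpoint, assumed 50% v 40% responders:* the base OR is 1.500. Dropping one topiramate non-responder gives 1.493; dropping one erenumab non-responder gives 1.508.

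**The case against.** **The affected groups may be almost empty.** To be dropped, a topiramate-arm patient must take no tablet at any time in the epoch; a missed first evening is not enough, and weekly visits follow. For that patient to be an event, an adverse-event discontinuation must be recorded after a placebo injection alone. Wrong-arm dosing should be rare, since packs are assigned by medication number through the IRT (Protocol 5.5.2). This stands, and it limits the expected size.

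***Active* may be loose wording for study drug.** This also stands. A reader might infer that the SAP will discard topiramate patients, or that the result is biased in a known direction. The documents do not support that: the SAP's own first-dose definition points both ways, the mirror case exists in the erenumab arm, and the odds ratio moves either way depending on whether the dropped patient had an event.

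**An as-treated set is defensible for a tolerability endpoint, and irrespective of adherence need not refer to grouping.** That is fair as a design argument. It does not remove the disagreement between the documents, and the reference to allocated treatment in Protocol 9.3.1 leans towards grouping as randomised.

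**Blacked-out text may explain the change of set.** Parts of Amendment 2, of the SAP after 2.5.3 and of the SAP after 2.14 cannot be read, so the change cannot be called undeclared. A hidden rationale would still leave the visible wording of Protocol 9.3.1, SAP 2.2 and SAP 2.5.1 in conflict.

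**Conclusion.** The conflict over the primary set is real and needs no special reading: the protocol says SAF as treated, the SAP says FAS as randomised. It matters only for patients who received the wrong arm's drug. The entry-rule point is secondary. It is an ambiguity that becomes unequal exclusion only if *active* means non-placebo, for a number of patients that is unknown and probably very small.

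Two stronger inferences should be avoided. One is that the choice will alter the trial's result: at an assumed 5% v 10%, no one-patient case crosses 0.05. The other is that it cannot: at an assumed 10% v 15%, regrouping one topiramate event or dropping two does cross it, though this takes a result already near the threshold. Both rest on assumed rates and an unadjusted odds ratio. Nor is the primary p-value the only one that carries a claim, since SAP 2.6.2 also claims superiority at 5% for the secondary endpoint. Both documents name the FAS for that endpoint, so only the entry rule bears on it.

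This should be fixed: the likely effect is small, but so is the cost.

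**What to change.** Before unblinding:

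- **Primary set.** Name one set in both Protocol 9.3.1 and SAP 2.5.1. The FAS as randomised is preferable, with the SAF as treated as supportive. This needs a written amendment to 9.3.1, approved by the sponsor, the IRB/IEC and, where required, health authorities (Protocol 11.1). Aligning SAP 2.5.1 to the protocol's SAF would need only a SAP edit, but would keep an as-treated primary comparison.
- **SAP 2.2, FAS.** Restore the protocol's rule: *all randomised participants who received at least one dose of any double-blind study medication (syringe or tablet, active or placebo), analysed as randomised.*
- **SAP 2.1.1.1, First IMP Dose Date, first sentence.** Replace the reference to verum with *double-blind test- or control-IMP, active or placebo*, so that it agrees with the second sentence.
- **SAF.** Use one entry rule in both documents and state how a patient who received only placebo components is assigned. Requiring an active dose for an as-treated safety set is defensible if both documents say so.

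The cost is a few SAP sentences and, for the preferred option, one protocol amendment. No new data and no change in sample size are needed.

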### **2.2.1 Subgroup of interest**

Subgroup analyses are planned only for the primary endpoint (see [Subgroup analyses](#)).

## **2.3 Patient disposition, demographics and other baseline characteristics**

### **2.3.1 Patient disposition**

Screening and baseline epoch patient disposition will be based on all screened patients data.

A patient disposition summary for the screening and baseline epoch will include number and percentage of patients, concerning

- Screening  
A patient is defined as screened if signed informed consent is available
- Screening failure  
A patient is defined as screening failure if he was screened but not randomized
- Randomization  
Subjects are considered randomized if they have been assigned a randomization number.
- Non-randomization
  - Reason for non-randomization

The total number of patients screened and the number of patients with screening failure will be summarized, including the reason for screening failure.

The reason for non-inclusion into the study will be listed for screened/baseline patients who discontinued from study prior to randomization.

Patient disposition for the DBTE and follow-up epoch will be presented based on the randomized set (RS).

A corresponding summary will include number and percentage of patients (treatment group specific and overall), concerning

- Completion of double-blind treatment  
A patient is defined as completer for the double-blind treatment if double-blind treatment completion status on the eCRF page is ticked as not prematurely discontinued
- Discontinuation of double-blind treatment
  - Reason for discontinuation of double-blind treatment
- Study completion  
A patient is defined as completer for the study if study completion status on the eCRF page is ticked as not prematurely discontinued
- Discontinuation of the study
  - Primary reason for discontinuation of the study

Protocol deviations (PDs) will be summarized separately for PDs not related to COVID-19 and for PDs related to COVID-19. For PDs not related to COVID-19, the number of patients with at least one PD will be presented (based on RS) and the results of the PDs will be grouped using

the broad categories (Inclusion/Exclusion Criteria (Study eligibility), Withdrawal criteria met, but subject not discontinued, Treatment Deviation, Prohibited Concomitant Medication, Other). For PDs related to COVID-19, the number of patients with at least one PD will be presented (based on RS) and the results of the PDs will be grouped by category of COVID-19 PD and type of relationship to COVID-19.

The number of patients within each of the analysis sets (RS, FAS, SAF) used in the study will be given.

### 2.3.2 Demographic variables and other baseline characteristics

Demographic variables and other baseline characteristics including previous migraine treatments will be summarized for each randomized treatment group and for all participants (total) using FAS.

For continuous variables mean, median, standard deviation, minimum, and maximum will be reported, whereas for categorical variables the number and percentage of participants in each category.

**Patient demographic data** includes age (years), sex, race, weight (kg), height (cm), BMI (kg/m^2), and source of patient referral.

**Baseline disease characteristics** contain following information assessed at baseline (see Section 2.1.1.1 for baseline definition):

- Monthly migraine days
- Monthly headache days
- Acute headache medication (none vs. migraine-specific vs. non migraine-specific)
- Prior treatment failure status (naïve vs. prior treatment failure, related to the prophylactic migraine treatments propranolol/metoprolol, amitriptyline, flunarizine)
- Beck Depression Inventory - II (BDI-II, minimal depression (0-13) vs. mild depression (14-19))

### 2.3.3 Medical history

Relevant medical history/current medical conditions present before signing the Informed consent will be recorded on the 'Medical History' eCRF page.

**General medical history** data includes medical history term, which will be summarized by system organ class and preferred term in the MedDRA dictionary.

**Medical history possibly contributing to liver dysfunction** data includes medical history term, which will be summarized by system organ class and preferred term in the MedDRA dictionary.

**Headache and migraine frequency history** data includes frequency of migraines over the past 3 months before screening (average days per month subject had migraines), frequency of headache (migraine and non-migraine) over the past 3 months before screening (average days per month subject had headache) and patient's age at migraine onset.

## 2.4 Treatments (study treatment, rescue medication, concomitant therapies, compliance)

### 2.4.1 Study treatment / compliance

The analysis of study treatment data will be based on the SAF.

For Control-IMP (topiramate or placebo):

- dose level distribution (number and percent of patients with particular dose) per visit in the titration phase summarized by treatment group
- duration of exposure out of tapering off phase summarized descriptively by treatment group
- duration of exposure including tapering off summarized descriptively by treatment group

For Test-IMP (AMG 334 or placebo):

- Number and percentage of patients receiving 1/2/3/4/5/6 doses of Test-IMP summarized by treatment group
- Duration of exposure summarized descriptively by treatment group
- Number and percentage of patients with starting dose of 70 mg or 140 mg.
- Reason for starting dose of 140 mg
- Number and percentage of patients with dose change from 70 mg to 140 mg and the corresponding reason

### 2.4.2 Prior, concomitant and post therapies

Number and percentage of patients with **prior prophylactic migraine treatment failure** will be presented based on RAS. A summary will be done for each failed treatment category with the primary reason for treatment discontinuation specified.

The number and percentage of patients receiving acute medications (during baseline and double-blind treatment epoch) will be reported. The number and percentage of patients receiving concomitant medications and significant non-drug therapy (during the double-blind treatment period) will be summarized by ATC level 1 and preferred name (coded by WHO Anatomic Therapeutic Chemical classification [ATC]) and by treatment group.

The use of concomitant medications and significant non-drug therapy during the follow-up period will be summarized in the same way, in a separate table.

## 2.5 Analysis of the primary objective

The primary objective of the study is to demonstrate the tolerability of erenumab compared to topiramate assessed by the rate of patients discontinuing treatment due to AE during the double-blind epoch of the study.

### 2.5.1 Primary endpoint

The primary endpoint of the study is discontinuation of treatment due to AE during the double-blind epoch of the study.

Analysis on primary endpoint should be done based on Full Analysis Set (FAS).

### 2.5.2 Statistical hypothesis, model, and method of analysis

Null hypothesis: odds of AE-related treatment discontinuations are equal in both treatment groups

Alternative hypothesis: odds are not equal when comparing erenumab to topiramate

Statistical hypothesis:

$$H_0: (p_1 / (1 - p_1)) / (p_0 / (1 - p_0)) = 1,$$

where

$p_j$  –probability of AE-related treatment discontinuations for the treatment group  $j$

$j = 0$  corresponds to topiramate group

$j = 1$  corresponds to erenumab group

The odds ratio not significantly different from one would mean that there is no evidence for a difference in AE-related treatment discontinuations between the two treatment groups.

Statistical hypothesis will be tested in the frame of logistic regression analysis controlling for the stratification factor (4-7 vs. 8-14 vs.  $\geq 15$  MMD at baseline):

$$\text{logit}(\text{proportion}) = \text{treatment group} + \text{stratification factor}$$

Odds ratio, its 95% confidence interval and the corresponding p-value will be presented. Significance level will be set at 5%. By significant test results ( $p(\text{odds ratio} = 1) \leq 0.05$ ) the superiority of erenumab will be claimed only by the correct direction, i.e. if the erenumab odds are lower than topiramate odds.

Additionally to the odds ratios, estimates for the relative risk and the risk difference (with 95% confidence intervals and p-values) will be calculated for the primary endpoint. Confidence intervals and p-values for the relative risks and risk difference will be calculated based on the normal distribution.

In case of zero events in only one treatment arm add 1 patient with 0.5 events to each treatment arm for calculation of the relative risk. Odds ratio will not be estimated in this case.

In case of zero events in both treatment arms no odds ratio will be estimated, the null hypothesis will not be tested and no difference between treatment arms can be claimed. Additionally, no relative risk will be calculated.

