End of trial will occur when the last patient completes last visit (LPLV).

Figure 1-1 Study Design

Patients will be stratified into groups according to their number of migraine days during the baseline epoch (4 - 7 vs. 8 - 14 vs.  $\geq 15$  monthly migraine days).

[figure not shown]
The study will recruit approximately 375 patients per arm (750 total) including up to a maximum of 35 patients with  $\geq 15$  monthly migraine days per arm (approx. 10 % of patients per arm). Assumptions were based on clinical studies with topiramate and erenumab.

No interim analysis is planned.

[figure not shown]

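### If exactly one arm has no AE discontinuations, SAP 2.5.2 drops the odds ratio that carries the primary claim and does not say which test decides (minor)

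*SAP*

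**What the plan says.** Protocol 9.3.2 and SAP 2.5.2 define one route to the primary claim. In the SAP: "Statistical hypothesis will be tested in the frame of logistic regression analysis controlling for the stratification factor". In the protocol: "The null hypothesis of equal odds will be rejected if the 2-sided p-value from the logistic regression model" for the treatment factor is below 0.05, with superiority claimed only if the odds are lower under erenumab. Neither text says whether that p-value is of Wald, score or likelihood-ratio type.

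SAP 2.5.2 then gives two sparse-data rules:

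- **Zero events in one arm only:** each arm is enlarged by a single patient who contributes half an event, and this is done for the relative risk alone. On the odds ratio the rule is "Odds ratio will not be estimated in this case". No other test is named.
- **Zero events in both arms:** no odds ratio, and "the null hypothesis will not be tested and no difference between treatment arms can be claimed".

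The same section plans a relative risk and a risk difference with normal-approximation intervals and p-values, presented as additions to the odds ratio. The half-event correction is attached to the relative risk only, so the risk difference stays uncorrected. Nothing says that either measure may carry the primary claim.

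On subgroups, SAP 2.2.1 says "Subgroup analyses are planned only for the primary endpoint". Their definitions and methods are not visible in the public text.

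**The concern.** The plan foresees the one-arm case and writes a rule for it. The rule withholds the quantity on which the decision rests and leaves the decision unassigned. The contrast with the both-arms rule sharpens this. That rule states that the hypothesis goes untested. The one-arm rule is silent, which suggests that some test remains without saying which.

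Two or three p-values would then be on the table, possibly on opposite sides of 0.05, and the choice between them would be made with the results known. Protocol 1.2 says the data will also support health technology assessments and reimbursement negotiations. A primary claim resting on a test chosen afterwards, without an odds ratio or interval, would be easy to challenge there.

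**Working it through.** **Inputs.** SAP 1.1: about 375 patients per arm, 750 in total, "including up to a maximum of 35 patients with" at least 15 monthly migraine days per arm. Protocol 5.2: 1:1 allocation. Two-sided 5% level. The plan's own arithmetic holds: 2 × 375 = 750, and 35/375 = 9.3%, in line with its figure of about 10%. The sample size itself cannot be reproduced because the visible text gives no event rates or power. The rates below are therefore assumptions.

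**How likely is the case?** P(no events in an arm) = (1 − p)^n.

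| Assumed erenumab rate | n = 375 |
|---|---|
| 0.5% | 0.995^375 = 15% |
| 1% | 0.99^375 = 2.3% |
| 2% | 0.98^375 = 0.05% |

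The protocol summary gives 700 patients, not 750. With n = 350 the chance is 3.0% at 1% and 0.08% at 2%, so nothing changes.

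**What do the remaining measures say for 0/375 versus 8/375?**

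- Relative risk with the SAP's correction: RR = (0.5/376)/(8.5/376) = 0.059; ln RR = −2.833; SE = √(1/0.5 − 1/376 + 1/8.5 − 1/376) = 1.453; z = −1.95; **p = 0.051**.
- Risk difference, unpooled: 8/375 = 0.0213; SE = √(0.0213 × 0.9787/375) = 0.00746; z = 2.86; **p = 0.004**. The empty arm contributes no variance.
- Fisher's exact test: 2 × (375 × 374 × … × 368)/(750 × 749 × … × 743); **p = 0.0075**.

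The same calculations for other comparator counts, with the unadjusted likelihood-ratio test added:

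| Events, 0 versus | Corrected RR | RD | Fisher | Likelihood ratio |
|---|---|---|---|---|
| 3 | 0.198 | 0.082 | 0.249 | 0.041 |
| 4 | 0.140 | 0.044 | 0.124 | 0.018 |
| 6 | 0.080 | 0.014 | 0.031 | 0.004 |
| 8 | 0.051 | 0.004 | 0.0075 | 0.0008 |
| 9 | 0.042 | 0.002 | 0.004 | 0.0004 |

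Relative risk and risk difference fall on opposite sides of 0.05 for 4 to 8 comparator events. From 9 events on, all four are below 0.05.

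**Does the planned model settle it?** Not as specified. With illustrative strata of 130, 210 and 35 per arm and 0 versus 6 events, maximum-likelihood logistic regression does not converge to a finite treatment coefficient (about −22, SE about 18,000) and its Wald p-value is 0.999. The unadjusted likelihood-ratio p-value for the same counts is 0.004. The type of p-value therefore determines the answer, and the plan does not state it.

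**Does the choice of replacement matter?** Yes. For 0 versus 5 of 375 with the same strata, Firth-penalised logistic regression gives a penalised likelihood-ratio p = 0.027, while unstratified Fisher, used here as a proxy for an exact test, gives 0.062. The plan should name one method, not a choice of two.

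**The case against.** **The SAP does not refuse to test.** A reader might infer that the primary hypothesis cannot be tested when one arm is empty. The text does not say so. It rules out testing only when both arms are empty, and a likelihood-ratio or score p-value can still be obtained from the logistic model. This objection stands: the defect is an unassigned decision.

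**Valid comparisons remain.** One might also think that the only fallback is a weak, corrected relative risk. The risk difference is planned too, is uncorrected, and gives p = 0.004 for 0 versus 8. So low power is a feature of the corrected relative risk, not of everything left. This stands, but both measures are labelled additional, so the question of which one decides is still open.

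**The case is remote.** It needs a true erenumab rate of about 1% or less. Disagreement across 0.05 between the two planned measures also needs only 4 to 8 comparator events, about 1% to 2% of 375, although Protocol 3.2 rests the design on high discontinuation rates for existing treatments. With 20 or more comparator events even the corrected relative risk has p < 0.01. This stands and sets the priority.

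**Subgroups.** It is tempting to say that small subgroups will meet the same rule. In an arm of 35 the chance of no events would be 0.98^35 = 49% at 2%, 0.95^35 = 17% at 5% and 0.90^35 = 2.5% at 10%. But subgroup definitions and methods are blacked out. It cannot be seen whether the stratum with at least 15 migraine days is a subgroup or whether this rule applies there. A subgroup would in any case lose an estimate, not the primary test.

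**Secondary endpoint.** SAP 2.6.2 repeats the sentence, but reaching it needs an arm without a single 50% responder. At the 13.7% placebo rate quoted in Protocol 1.1 for the LIBERTY study, 0.863^375 is about 10^−24. Nothing should be built on that.

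**Conclusion.** The point holds in a narrow form: with zero events in exactly one arm, the primary decision rule is undefined, and the deciding p-value would be chosen after unblinding. The planned additional measures can give opposite answers at 5%, as 0/375 versus 8/375 shows.

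Priority is **minor**. The probability of reaching the case rests on assumed erenumab rates and falls from 15% at 0.5% to 0.05% at 2%. The Wald, relative-risk, risk-difference and Fisher results do not depend on those rates, only on the event counts and about 375 patients per arm. The strata used for the logistic fits are illustrative. The documents do not support a claim that the trial would be unable to declare a clear tolerability difference, or that subgroup results are known to be affected.

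**What to change.** In SAP 2.5.2, replace the sentence withholding the odds ratio with:

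*If exactly one arm has zero events, the treatment odds ratio, 95% profile-likelihood confidence interval and p-value are obtained from Firth-penalised logistic regression with treatment and stratification factor, and the penalised likelihood-ratio p-value is the primary test.*

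The test should be the one that the profile interval inverts (same penalty, treatment coefficient set to zero), so that interval and p-value agree. Apply the rule to any subgroup analysis of the primary endpoint that uses this model. The relative risk correction and the both-arms rule can stay as they are.

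The cost is one sentence and one model option, with a little code for the penalised likelihood-ratio p-value. Because it is triggered only by zero events in one arm, every other analysis is unchanged. It should be in place before unblinding.
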